9.2.1.1 Supportive Analyses of the Primary Efficacy Analysis

A secondary (supportive) analysis to the primary method for the analysis of the primary efficacy measure will be conducted using the per-protocol population, according to randomized treatment group. For this analysis, LS means, 95% CIs of the LS means, SEs of the LS means, LS mean estimate of the treatment difference (MS1819-SD minus porcine PERT), SE of the difference, and 95% CI of the difference will be displayed.

9.2.1.2 Subgroup Analyses

Subgroup analyses comparing MS1819-SD to porcine PERT using CFA at the end of each treatment period as the dependent variable will be performed for:

- CFA level while receiving porcine PERT (<80%, ≥80%)
- Gastric acid suppression use (yes, no)

The primary efficacy endpoint analysis will be repeated for each subgroup using the mITT population, according to randomized treatment group. For the gastric acid suppression use subgroup, gastric acid suppression use will be removed as a covariate from the model. For each analysis, LS means, 95% CIs of the LS means, SEs of the LS means, LS mean estimate of the treatment difference (MS1819-SD minus porcine PERT), SE of the difference, and 95% CI of the difference will be displayed for each subgroup.

In addition, CFA for each subgroup will be summarized by treatment group using descriptive statistics.

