**Efficacy Analysis:**

- **Primary Efficacy Endpoint**

- **Primary Model of Analysis:** The primary endpoint (ie, the CFA assessed at the end of each 3-week treatment period [Visit 6 or Visit 9]), will be analyzed in a mixed model including terms for sequence (MS1819-PERT vs PERT- MS1819); random patient nested in sequence; period (1 vs 2); and treatment (MS1819 vs porcine PERT). The treatment effect, along with the 95% confidence interval (difference in adjusted CFA means, MS1819 minus porcine PERT), will be estimated in this model. Noninferiority will be claimed if the lower bound of the 95% confidence interval is greater than -15%, where 15% is the noninferiority margin. If noninferiority can be claimed, then superiority will be tested.

**Subgroup Analyses:** Analyses of CFA considering the same approach used for the primary set will be performed in the following subgroups:

- by CFA level while receiving porcine PERT (<80% vs  $\geq 80\%$ ). Of note, it is expected that about 75% of enrolled patients will have CFAs while receiving porcine PERTs of 80% or greater. An analysis will be done in the subgroup of patients with CFA below 80% while receiving porcine PERT, as well as in the subgroup of patients with CFA of 80% or greater while receiving porcine PERT.
- By those receiving or not receiving gastric acid suppression

- **Key Secondary Efficacy Endpoints**

- Stool weights, and signs and symptoms of malabsorption will be analyzed with the same approach used for the primary endpoint, switching non-parametric and semi-parametric methods employed in the case that model assumptions are violated.

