- Incomplete correction of the lipid malabsorption, which can only be reached by high doses of enteric coated enzyme therapy in approximately 50% of patients with EPI caused by chronic pancreatitis and/or pancreatectomy [Dominguez-Munoz et al, 2006; Safdi et al, 2006]. An internal survey based on all publicly available individual data show that only 25% of patients affected by CF with EPI had fully normalized coefficient of fat absorption (CFA) (ie, CFA higher than 93%) on porcine PERT substitution therapy. The incomplete enzymatic activity of porcine PERTs in the physiochemical environment of the upper digestive tract explains their reduced efficacy. A number of factors are involved, including the gastric acid pH in the range of 1 to 4; the intestinal pH ranging from 4 to 6 (porcine PERTs are active at pH > 6.5 in presence of biliary salts); and the protease content of the upper digestive tract (i.e., gastric pepsin).
- The hazard of zoonotic pathogen transmission to humans remains possible with porcine PERTs because of their animal origins. For example, the porcine parvovirus may be present in these extracts, with (minimal) risk that it can cross species and transmit diseases to humans (Cherney, 2008).

- Most pancreatic enzyme products are unstable. To compensate for enzyme degradation over time, most manufacturers currently include overfill in the finished product. Therefore, their composition is poorly standardized and results in large 'lot-to-lot' variation of efficacy and composition. As product instability requires the product to be stored at cool temperatures, efficacy can decrease once the bottle is open (eg, 6 months for Creon®).
- Some additional concerns identified with porcine PERTs include irritation of oral mucosa if chewed/retained and hyperuricemia because of the presence of purines in porcine pancreatic extracts [Package insert Creon, Pancreaze, Zenpep, Pertzye]. In addition, patients with an allergy to proteins of porcine origin may have severe allergic reactions.
- Because all of the currently marketed PERTs are porcine derived, there is a supply risk (both quality and quantity) that is dependent on the availability of pig herds.

Because of the risks and limitations of porcine PERT, new drugs are demanded by pharmaceutical regulatory agencies and patient associations.

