#### 8.1.1 Visit 1, D-21 to D1: Screening Visit

The following procedures will be performed at the Screening Visit (which may take place over more than one day):

- Obtain signed informed consent from the patient before any study-related assessments are made
- Collect relevant medical history, including concomitant illnesses/diseases, previous/concomitant medications, and record AEs
- Complete physical
- Specific CF assessment including a pulmonary function test by spirometry to determine FEV1 >30% of predicted normal for age, sex, and height at screening and a sweat chloride test
- Record body height and weight
- Record vital signs while sitting (blood pressure, pulse rate, breathing rate, and temperature)
- Assess for eligibility (against the inclusion and exclusion criteria)
- Record demographic data such as ethnic origin, date of birth, and sex
- Collect urine sample for urinalysis
- Perform a serum pregnancy test, if applicable
- Collect samples for hematology, clinical chemistry, PT/INR, activated partial thromboplastin time (aPTT)
- Collect blood samples for vitamin determination (A, D, E, and K)

- Patients will be required to fast before the collection of screening laboratory tests.
- Collect samples for fasting lipids and prealbumin
- Obtain a stool sample for fecal pancreatic elastase concentration in the selected central laboratory

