### **Secondary Analysis:**

The same analysis as described above will be performed in the PP set.

**Subgroup analyses:** Analyses of CFA considering the same approach used for the primary set will be performed in the following subgroups:

- by CFA level while receiving porcine PERT (<80% vs  $\geq 80\%$ ). Of note, it is expected that about 75% of enrolled Patients will have CFAs while receiving porcine PERTs of 80% or greater. An analysis will be done in the subgroup of Patients with CFA below 80% while receiving porcine PERT, as well as in the subgroup of patients with CFA of 80% or greater while receiving porcine PERT.
- By those receiving versus not receiving gastric acid suppression.

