9.2 Analysis Methods

9.2.1 Primary Efficacy Analyses

The primary efficacy endpoint is the CFA assessed at the end of each 3-week treatment period (Visit 6 or Visit 9). CFA is evaluated by the 72-hour marker-to-marker stool sample collection (1 measure at Visit 6 and 1 at Visit 9) and standardized high-fat diet during each supervised confinement. Coefficient of fat absorption represents the percentage of fat absorbed from the diet by the subject and is calculated from the results of the quantitative fecal fat measurement in conjunction with the dietary fat intake.

CFA will be calculated by using 2 data points:

- Fat consumption in grams as provided by the qualified dietitian at each site.
- Fat excretion in grams/24h as provided by the central laboratory.

CFA will be calculated as follows:

$$\frac{(\text{Grams/24h of fat consumed} - \text{Grams/24h of fat excreted}) \times 100}{\text{Grams/24h of fat consumed}}$$

The primary efficacy endpoint analysis will use the mITT population and be analyzed as randomized. For the analysis of CFA, if a subject switches study treatments (i.e. MS1819 to PERT or PERT to MS1819) during the confinement period, prior to the end of the stool collection, then the CFA value during that confinement period will be excluded from the analysis. The primary method for the analysis of the primary efficacy endpoint will be based on a mixed model. Missing CFA values will not be imputed.

The mixed model will include terms for sequence (MS1819-PERT, PERT-MS1819), random patient nested in sequence, period (1, 2), treatment (MS1819, PERT), and gastric acid suppression use (Y, N). The mixed model will be implemented using SAS® Proc MIXED, as shown in the model code below. The DDFM=KR option denotes the Kenward-Roger method for the denominator degrees of freedom. The variable GASTFL in the code below is the gastric acid suppression use flag (Y, N).

```
PROC MIXED;  
  CLASS SUBJECT SEQUENCE PERIOD TREATMENT GASTFL;  
  MODEL CFA = SEQUENCE TREATMENT PERIOD GASTFL /  
    DDFM=KR;  
  RANDOM SUBJECT(SEQUENCE);  
  LSMEANS TREATMENT / CL DIFF;  
  RUN;
```

The 95% CI of the difference in CFA for MS1819-SD minus CFA for porcine PERT will be used to assess the primary objective. Non-inferiority of MS1819-SD to porcine PERT is achieved if the lower bound of the 95% CI of the difference is greater than -15%,

where 15% is the non-inferiority margin. If non-inferiority is achieved, then superiority will be tested.

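### The subgroup split on CFA under porcine PERT uses the PERT-period outcome itself, so its two MS1819-minus-PERT differences are biased in opposite directions

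*SAP*

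**What the plan says.** SAP 9.2.1.2 names two subgroup factors for the CFA comparison: gastric acid suppression use, and "CFA level while receiving porcine PERT" cut at 80%. The primary mixed model is refitted in each part. For each part the "LS mean estimate of the treatment difference (MS1819-SD minus porcine PERT), SE of the difference, and 95% CI of the difference will be displayed". The section adds that "CFA for each subgroup will be summarized by treatment group using descriptive statistics".

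Protocol 10.7.1 and the synopsis plan the same split. The synopsis states: "An analysis will be done in the subgroup of patients with CFA below 80% while receiving porcine PERT", and likewise for patients at 80% or more. Protocol 10.7.1 gives the anticipated split: "it is expected that about 75% of enrolled Patients will have CFAs while receiving porcine PERTs of 80% or greater".

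On measurement, SAP 9.2.1 provides one CFA value at Visit 6 and one at Visit 9. The stool procedure at screening in Protocol 8.1.1 is: "Obtain a stool sample for fecal pancreatic elastase concentration in the selected central laboratory". The baseline characteristics in SAP Section 6 include no CFA. Neither document names another source for CFA on PERT, cautions about the split or plans a correction.

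**The concern.** Each patient has two CFA values, one per treatment. The PERT value decides which subgroup the patient enters, and it is also the value subtracted to form the treatment difference. Patients fall below 80% partly because their PERT reading was low by chance on that occasion. Their MS1819 reading does not share that chance error, so MS1819 minus PERT is pushed upward. At or above 80% the opposite happens. This is regression to the mean built into the definition of the subgroup, and it does not need any true difference in effect between poor and good PERT responders.

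What is at stake is interpretation. The two estimates can look like effect modification by PERT response. Protocol 5.3 raises possible use of a lipase in patients who respond poorly to porcine enzymes, and Protocol 5.6.2 reports a trend to an inverse relation between response and baseline CFA. A favourable figure below 80% could readily be read as confirming both.

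**Working it through.** **Inputs from the documents**
- Share expected below 80% on PERT: 25% (Protocol 10.7.1), about 7.5 of 30 completers.
- SD of paired differences 20, margin 15, expected difference -8, difference used for power -4, 30 completers (SAP 2.6).
- A quarter of CF patients on PERT above 93%, from an internal survey in a different population (Protocol 5.3).

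**Assumed, because the documents do not give it:** the reliability of a single CFA on PERT, meaning the share of its variance that is repeatable and carries over to the MS1819 value. I use 0.3, 0.5 and 0.7.

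**The plan's own power figure.** Standard error 20/√30 = 3.65; distance to the margin 15 - 4 = 11. With a t test on 28 degrees of freedom, power is 82.8%, consistent with the stated figure of around 80%. The SD of 20 is therefore used as the plan uses it.

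**Step 1: size of the selection.** For a normal distribution cut at its lower quartile, the density at the cut is 0.3178. The mean of the lower part lies 0.3178/0.25 = 1.271 SD below the overall mean. The mean of the upper part lies 0.3178/0.75 = 0.424 SD above it. Hence
- bias below 80% = +1.271 × (1 - reliability) × SD of CFA on PERT
- bias at or above 80% = -0.424 × (1 - reliability) × SD of CFA on PERT

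For an assumed SD of 8 to 12 and reliability 0.5, this is +5.1 to +7.6 and -1.7 to -2.5 points. Weighted by 25% and 75%, the two biases cancel, so the overall estimate is unaffected.

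**Step 2: an SD tied to the documents.** Quartiles at 80 and 93 give a mean of 86.5 and an SD of 6.5/0.6745 = 9.64. The means of the two parts are 74.3 and 90.6. This normal curve puts 8% above 100%, so a beta curve bounded at 0 and 100% with the same quartiles was used as a check (mean 85.5, SD 9.8, part means 71.7 and 90.1).

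| Assumed reliability | 0.3 | 0.5 | 0.7 |
|---|---|---|---|
| Bias below 80%, normal | +8.6 | +6.1 | +3.7 |
| Bias at or above 80%, normal | -2.9 | -2.0 | -1.2 |
| Bias below 80%, bounded | +9.6 | +6.9 | +4.1 |
| Bias at or above 80%, bounded | -3.2 | -2.3 | -1.4 |
| Shown below 80% if the true average is -8 in both parts (normal) | +0.6 | -1.9 | -4.3 |
| Shown at or above 80%, same case (normal) | -10.9 | -10.0 | -9.2 |

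**Step 3: sensitivity to how the SD of 20 is explained.** An SD of 9.64 on PERT and 20 for the differences cannot come from a constant effect with equal error in both periods. That would need an error SD of 20/√2 = 14.14, more than the whole PERT SD. The figures in Step 2 therefore imply larger error on MS1819 or real variation in response. If the SD of 20 is instead put down to equal within-patient error with a constant effect, the bias is 1.271 × 200/SD below 80% and 0.424 × 200/SD at or above. For an assumed PERT SD of 14.15 to 25 that gives +18 to +10 and -6.0 to -3.4 points. With a within-patient SD of only 5 and a between-patient SD of 10, it is about +2.8 and -0.9.

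**Step 4: is the classifier the cause?** Patients were simulated with a constant effect of -8, between-patient SD 10 and within-patient SD 14.14. Classified on the PERT-period value, the two parts gave +6.7 and -12.9. Classified on a separate PERT measurement, which this trial does not collect, the same patients gave -7.9 and -8.0.

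**Step 5: if someone applied the -15% rule below 80%.** This used 60,000 simulated trials of 30 completers, 15 per sequence, under the normal curve of Step 2 with an SD of differences of 20. The estimate was the average of the two sequence means of within-patient differences. For complete pairs this matches the planned model, because the patient-level gastric acid term cancels. At a true average of -15, the lower limit cleared -15% in about 17%, 10% and 6% of trials at reliability 0.3, 0.5 and 0.7. At reliability 1.0 it did so in about 2.4%, close to the nominal 2.5%. The median half-width of the interval was about 17 to 18 points.

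**The case against.** The strongest case against acting is that no decision hangs on this table. The SAP states no noninferiority claim and no interaction test by subgroup. Protocol 10.1 does not expect inferential significance at this sample size, and SAP 2.6 says the sample size was chosen mainly for safety. With seven or eight patients below 80%, a bias of +3.7 to +8.6 is at most about half the interval's half-width. The size also rests on an SD and a reliability that appear nowhere in the documents, and other reasonable assumptions move it from about +3 to +18. The observed means do correctly describe the observed strata, and true variation in response could mask the pattern. A caution attached to the existing table might be enough.

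Most of this stands and limits the severity: the risk is to interpretation, and only the existence and direction of the bias are firm. Two parts do not carry. Imprecision does not remove bias, since each interval is centred on a shifted value. A caution alone would still leave a prespecified estimate and interval on display that do not estimate the treatment effect in poor or good PERT responders. A scatter plot shows regression to the mean as well, but it presents no stratified treatment effect.

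**Conclusion.** The concern holds and should be fixed. The only CFA on PERT in the schedule is the PERT-period outcome, so the split conditions on one half of the treatment difference. Relative to the effect in patients whose usual CFA on PERT is truly below or above 80%, the lower part is biased towards MS1819 and the upper part towards PERT. This needs only some within-patient variability in CFA. An illustrative size is +3.7 to +8.6 points below 80% and -1.2 to -2.9 at or above. That rests on the 25% share, normal quartiles at 80 and 93, and an assumed reliability of 0.3 to 0.7. Confidence is high on existence and direction and low on size. The descriptive summary of CFA by treatment within this split carries the same bias. The primary analysis and the gastric acid suppression subgroup are not affected.

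**What to change.** In SAP 9.2.1.2, Protocol 10.7.1 and the synopsis, remove the LS-mean treatment difference, its confidence interval and any noninferiority reading for the split by CFA on PERT. Suggested text: *Individual CFA values on MS1819-SD will be plotted against those on porcine PERT. No treatment difference will be estimated by CFA level on PERT, because that level is the PERT-period outcome and regression to the mean is expected.* If the descriptive table by treatment is kept for this split, attach the same caveat to it. Limit comparative subgroup models to factors known before randomization, such as the gastric acid suppression subgroup already planned. If a different source of CFA on PERT was intended, the SAP must name it. Record the change in SAP 11.1.

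The cost is wording in three places, one log entry, and one table replaced by a plot. No new data are needed. The sponsor gives up the 80% cut as a comparative subgroup.

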## 10. STATISTICAL METHODS

### 10.1 General Considerations

**The statistical methods will be further detailed in the Statistical Analysis Plan (SAP).**

Any change to the data analysis methods described in the protocol will require an amendment only if it changes a principal feature of the protocol. Any other change to the data analysis methods described in the protocol, and the description for making the change, will be described in the SAP and in the clinical study report. Additional exploratory analyses of the data will be conducted as deemed appropriate.

Statistical methodology and analyses will be in accordance with the principles outlined by the International Council for Harmonisation (ICH) E9 guidelines.

Tables, listings, and figures will be produced in accordance with the principles outlined by the ICH E3 guidelines.

Summaries will consist of descriptive statistics including the nonmissing counts, mean, standard deviation, median, Interquartiles (IQ), minimum and maximum values for continuous variables, and number and percentage of patients in each defined category for categorical variables.

Statistical tests will be performed at a one-sided 2.5% alpha. However, for the purposes of simplicity and clarity, displays will utilize the equivalent two-sided 5% nominal significance level along with 95% two-sided confidence intervals (CI). The primary goal of the study is to establish the safety of the chosen dose level; with the sample size, it is not anticipated that inferential statistics will achieve significance.

There will be no adjustment for multiplicity arising from secondary efficacy analyses of the primary endpoint and/or secondary endpoint testing. The primary efficacy analysis of the primary endpoint aims to compare the efficacy of MS1819 vs porcine PERT.

As a general rule, missing data will not be replaced.

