2.6 Sample Size Determination

The primary objectives of the trial are to assess the safety of MS1819 and whether the efficacy of MS1819 is noninferior to porcine PERT. The sample size was primarily selected to be sufficient to address the safety objectives of this trial. Given the sample size, efficacy will be assessed with the understanding that adequate power for assessing efficacy would only be achieved for differences that are more favorable than expected.

With regard to safety assessment, at least 30 patients completing both periods are judged enough to adequately assess safety. Any event not occurring in the study would have a 95% CI on the rate extending from 0% to 10%; thus events not occurring may be assumed to be uncommon in the population (<10%).

With regard to efficacy, the primary objective is to show that the efficacy of MS1819, measured on the primary endpoint (ie, the CFA), is noninferior to porcine PERT.

- The noninferiority is chosen equal to 15% and the rationale for this choice is as follows: the difference in mean change from baseline in CFA between the reference and placebo was found to be approximately 32.6% in Trapnell (2011). According to the guidance on Noninferiority Clinical Trials to establish effectiveness (2016), the noninferiority (NI) margin should preserve a specified fraction of the difference between the reference and placebo. A NI margin of 15% preserves 54% of the estimated difference between the reference and placebo.
- In a recent unpublished trial, the standard deviation of the change in CFA was found to be around 16% among patients with a baseline CFA at or above 80%. As some patients enrolled in this trial might have a CFA under porcine PERT lower than 80%, a higher standard deviation of around 20% is expected.
- Because the patients enrolled in the trial are already stabilized on porcine PERT, it is expected that the difference in CFA means between MS1819 and porcine PERT slightly favors PERT, which is expected to be around -8%.

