Out of an abundance of caution, the planned sample size is limited to roughly 30 subjects completing. With regard to safety assessment, 30 patients completing both periods are judged enough to adequately assess safety. However, assuming a standard deviation of 20% for the paired differences in CFA measurements within each patient, a noninferiority margin of 15%, a more favorable than expected difference of -4.0% in CFA means between MS1819 vs porcine PERT that favors PERT, a sample size of 30 patients completing both periods will provide a power of around 80% to show noninferiority of MS1819 to porcine PERT at the 0.05 2-sided nominal 0.05 level of significance (that is, a one-sided alpha of 0.025). Accounting for a 20% dropout rate, 38 patients will be sufficient to achieve a power of at least 80%.

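### The acid-suppression subgroup analysis uses two separate models and never estimates whether the MS1819-minus-PERT difference in CFA depends on acid suppression

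*SAP*

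**What the plan says.** SAP 9.2.1.2 names two subgroup factors: CFA while on porcine PERT (below 80%, or 80% and above) and gastric acid suppression (yes, no). On method it says: "The primary efficacy endpoint analysis will be repeated for each subgroup using the mITT population, according to randomized treatment group". For the acid-suppression strata the covariate is removed from the model. The output for each subgroup is LS means, their SEs and intervals, and the treatment difference with its SE and 95% CI.

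Protocol 10.7.1 places the subgroups under its Secondary Analysis heading: "Analyses of CFA considering the same approach used for the primary set will be performed in the following subgroups".

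The primary model in SAP 9.2.1 has sequence, treatment, period and the acid-suppression flag GASTFL as fixed effects, with a random patient term. It has no product of treatment and GASTFL. The same section holds the decision rule: the lower 95% limit must exceed -15%, "where 15% is the non-inferiority margin", and superiority is tested next if noninferiority is met.

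On error rates, Protocol 10.1 says "Statistical tests will be performed at a one-sided 2.5% alpha" and "There will be no adjustment for multiplicity arising from secondary efficacy analyses of the primary endpoint and/or secondary endpoint testing".

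Neither document calls the subgroup analyses exploratory, rules out claims from them, or plans an estimate comparing the treatment difference between strata.

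**The concern.** The point of splitting by acid suppression is to learn whether MS1819 compares differently with PERT when gastric acid is suppressed. Two separate models give two differences and two intervals, but no estimate of how far the differences are apart and no interval for that gap. The main effect in the primary model does not supply it. Under Protocol 7.5 acid suppressants must not be changed or stopped during the study, so GASTFL is constant within a patient. It shifts both of that patient's CFA values alike and says nothing about the difference between them.

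In the absence of that estimate, a reader is likely to compare the two intervals with -15%. If one clears it and the other does not, the natural inference is effect modification. The protocol makes that inference tempting: section 5.5.1 puts optimal LIP2 activity at pH 4 to 6, and section 5.3 says porcine PERT is active above pH 6.5. A split of this kind could influence the choice of population for a later study (section 5.1 to 5.3 ends by saying that Phase 3 studies can be considered). The check below asks how often a split would arise when nothing differs between the strata.

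**Working it through.** **Inputs from the documents**
- One-sided alpha 0.025 (Protocol 10.1); margin 15 CFA points (SAP 9.2.1).
- SD 20: "assuming a standard deviation of 20% for the paired differences in CFA measurements within each patient" (SAP 2.6).
- True difference -4 for the power statement: "a more favorable than expected difference of -4.0% in CFA means between MS1819 vs porcine PERT that favors PERT" (SAP 2.6).
- True difference the sponsor expects: "which is expected to be around -8" percent (SAP 2.6).
- 30 completers (SAP 2.6).

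**Assumptions not in the documents**
- Acid-suppression strata of 15/15 or 10/20 completers.
- The same true difference in both strata.
- A reader applies the -15% rule to each stratum's 95% CI.

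**Step 1: the plan's own figure.** Power comes from a noncentral t with noncentrality (15 + d)·√n/20, where d is the true difference, and n - 2 degrees of freedom. At n = 30 and d = -4 the noncentrality is 11 × √30/20 = 3.01, and power is 82.8%, slightly above the stated figure of around 80%. By the same method 80% power needs 28 to 29 completers, so 30 is supported. At d = -8, power at n = 30 is 45.7%.

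**Step 2: chance that a single stratum passes**

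| n | d = -4 | d = -8 |
|---|---|---|
| 10 | 33.5% | 16.3% |
| 15 | 50.5% | 24.1% |
| 20 | 64.3% | 31.6% |

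**Step 3: chance that the two verdicts disagree.** The strata contain different patients, so P(disagree) = p₁(1 - p₂) + p₂(1 - p₁).
- 15/15, d = -4: 2 × 0.505 × 0.495 = 50.0%
- 10/20, d = -4: 0.643 × 0.665 + 0.335 × 0.357 = 54.7%
- 15/15, d = -8: 2 × 0.241 × 0.759 = 36.6%
- 10/20, d = -8: 0.316 × 0.837 + 0.163 × 0.684 = 37.6%

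A two-sided 5% test of the contrast between strata would signal a difference in 5% of such trials.

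**Step 4: sensitivity.** A 23/7 split gives 39.2% at -8 and 61.8% at -4. With a true difference of 0 and 15/15, the figure is 35.9% at SD 20 and 15.0% at SD 16 (the SD that SAP 2.6 cites for patients with baseline CFA of at least 80%).

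**Step 5: precision of the missing contrast.** SE = 20 × √(1/n₁ + 1/n₂). At 15/15 this is 7.3, with a 95% half-width of about 15 points. At 10/20 it is 7.7, with a half-width of about 16.

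**The case against.** The strongest reply is that SAP 9.2.1.2 never says a verdict will be declared within a subgroup. It lists estimates and intervals and names no margin. Where the SAP wants the 15% margin used beyond the primary test, it says so, as for CNA in 9.2.2.1. That stands: whether repeating the primary analysis brings the rule with it is left open. The disagreement figures therefore describe what a reader would find on applying the rule, not a decision the SAP is known to make.

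Two stronger readings are tempting, and the documents do not support them.
- A reader might infer that a split is the most likely outcome when the strata are alike. That is so at -4, which the SAP itself calls more favorable than expected. At the expected -8 with 15/15, neither stratum passes in 0.759² = 57.6% of trials, a split occurs in 36.6% and both pass in 5.8%. A split in one named direction is half as frequent at 15/15: about 18% at -8 and 25% at -4.
- A reader might infer that false claims exceed the stated alpha. If every true difference were -15 and each interval were read as a claim, at least one of the two acid-suppression strata would pass in 1 - 0.975² = 4.9% of trials. But the 2.5% is stated per test, no study-wide rate is promised, the primary test is untouched, and Protocol 10.1 openly declines adjustment for secondary analyses of the primary endpoint.

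It can also be said that removing GASTFL within a stratum is no fault, since it is constant there. That is correct. Finally, the contrast is imprecise, and a reader could work it out from the two reported differences and SEs. That is also true, but an interval as wide as the margin is itself the message that about 30 patients cannot settle the question, and the plan should report it directly.

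**Conclusion.** The plan omits the one estimate that the acid-suppression subgroup exists to provide. That follows from the model statement and the subgroup method, and depends on no assumption. The size of the likely misreading does depend on assumptions. With strata of 15/15 or 10/20, SD 20, equal true effects and the -15% rule applied by the reader, verdicts disagree by chance in about 37% to 38% of trials at -8 and 50% to 55% at -4. Other inputs move this, from 15% to 62% in the cases shown.

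The figures concern acid suppression only. They do not carry over to the split by CFA on PERT, which is defined by one of the two outcomes being compared, so that its differences are distorted by selection as well as by chance.

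The change should be made. It corrects a secondary analysis; the primary noninferiority conclusion and its error rate are not in question.

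**What to change.** In SAP 9.2.1.2, replace the two separate acid-suppression models with one model in the mITT population, with the same random patient term:

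`MODEL CFA = SEQUENCE TREATMENT PERIOD GASTFL TREATMENT*GASTFL / DDFM=KR;`

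Report the MS1819-minus-PERT difference with its 95% CI in each stratum, and the contrast between the two differences with its 95% CI.

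Add a statement covering all subgroups, including the split by CFA on PERT: results are exploratory, and neither the -15% rule nor the superiority test is applied within subgroups.

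The cost is one model term, one or two output statements and a sentence. The downsides are a wide contrast interval, about ±15 to ±16 CFA points, and that no noninferiority claim can be made for a subgroup.
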